2.1 Subject selection

In this work, up to 55 subjects will be enrolled at multiple sites, with the aim of 50 subjects completing the study.

2.1.1 Subject withdrawal and replacement

This study includes four clinical visits. Once the study consent form is signed, the subject is considered to be enrolled on the study. Subjects who have signed the consent form, but who have not completed the initial visit will usually be replaced. All subject data will be included in the final analyses unless there are strong grounds for exclusion; such grounds will be detailed in the final report.

2.1.2 Subject recruitment

Subjects will be recruited by one or more of following means:

1. Posting study details on The University of Manchester's 'Research Volunteers' website.
2. Correspondence to existing wearers on the Eurolens Research database of subjects.
3. Advertising through a variety of media via a format separately approved by Manchester UREC.
4. Advertisement at external sites.
5. Contacting existing patients at external sites.

2.1.3 Inclusion criteria

Subjects will only be eligible for the study if:

1. They are aged between 18 and 40 years and have capacity to volunteer.
2. They understand their rights as a research subject and are willing and able to sign a Statement of Informed Consent.
3. They are willing and able to follow the protocol.
4. They currently wear soft contact lenses or have done so in the past two years.
5. They have a spherical component of their contact lens prescription between Plano to - 6.00DS (inclusive).
6. They have a cylindrical component of their contact lens prescription between -0.75DC and -2.50DC (inclusive).
7. They can be satisfactorily fitted with the study lens types.
8. At dispensing, they can attain at least 6/12 distance high contrast visual acuity in each eye with the study lenses within the available power range.

9. They are willing to comply with the wear schedule (at least five days per week and for at least eight hours per day).
10. They own a wearable pair of spectacles.
11. They agree not to participate in other clinical research while enrolled on this study.

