2.6.1 Lenses

Details of the study lens are provided in Table 2. All lens types are CE marked. Initial lens selection will be as indicated by the manufacturer fitting guidelines.

	MyDay toric	DAILIES Total 1 toric
Manufacturer	CooperVision Inc	Acon
Material	Stenfcon A	Defcon A
EWC (%)	54%	Core Water Content (%) 33%; Surface Water Content (%) > 80%
BOZR (mm)	8.6	
Diameter (mm)	14.5	
Spherical powers (D)	Pano to -6.00	
Cylindrical powers (D)	-0.75; -1.25, -1.75; 10°, 20°, 70°, 80°, 90°, 100°, 110°, 160°, 170°, 180°	-2.25 10°, 20°, 90°, 160°, 170°, 180° 0°
Axes (degrees)		Lens parameters to be confirmed

Table 2: Study lenses.

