16. Using the fitting set, the second lens pair will be fitted according to the randomisation table [REDACTED] selecting the closest available lenses for the subject's prescription.
17. Procedures are repeated for the second lens pair, as outlined in steps 6 to 15 above.
18. The subject will be discharged, and the study lenses ordered. Subjects are allowed to wear their own lenses until the next visit.

Where possible, for a single subject, the same spherical and cylindrical BVPs should be ordered for the two lens types – the axis ordered may vary for the lenses due to the different stabilisation characteristics of the lenses. However, if the fitting process indicates that a different spherical and/or cylindrical BVP needs to be ordered, this will be permitted.

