4.3 Personnel

A series of horizontal black bars of varying lengths, representing a redacted list of personnel names.

Protocol amendment

[figure not shown]
Study title: The comparative clinical performance of two daily disposable toric contact lenses

The table below lists the changes to be implemented in this work:

New revision no.	Section/s to be Amended and details																											
1	
Both lenses are now available in all axes from 10 to 180 (10 degree steps)
 
Section 2.6.1 Lenses
 
Table 2: Study lenses now amended to reflect the change of study lenses.
 
  
 Name	MMDay toric	DAILIES Total1 for Astigmatism	
   
 Manufacturer	CooperVision Inc	Alcon	
 
 Material	Silafilcon A	Delefilcon A	
 
 EWC (%)	54%	Core water content 33%, surface water content >80%	
 
 BOZR (mm)	8.6	8.6	
 
 Diameter (mm)	14.5	14.5	
 
 Spherical powers (DS)	Plano to -6.00D	Plano to -6.00D	
 
 Cylinder powers (DC)	-0.75, -1.25, -1.75	-0.75, -1.25, -1.75	
 
 Axes (degrees)	10-180, 10 degree steps	10-180, 10 degree steps	
  
 
Table 1: Study lenses
	Name	MMDay toric	DAILIES Total1 for Astigmatism	Manufacturer	CooperVision Inc	Alcon	Material	Silafilcon A	Delefilcon A	EWC (%)	54%	Core water content 33%, surface water content >80%	BOZR (mm)	8.6	8.6	Diameter (mm)	14.5	14.5	Spherical powers (DS)	Plano to -6.00D	Plano to -6.00D	Cylinder powers (DC)	-0.75, -1.25, -1.75	-0.75, -1.25, -1.75	Axes (degrees)	10-180, 10 degree steps	10-180, 10 degree steps
Name	MMDay toric	DAILIES Total1 for Astigmatism																										
Manufacturer	CooperVision Inc	Alcon																										
Material	Silafilcon A	Delefilcon A																										
EWC (%)	54%	Core water content 33%, surface water content >80%																										
BOZR (mm)	8.6	8.6																										
Diameter (mm)	14.5	14.5																										
Spherical powers (DS)	Plano to -6.00D	Plano to -6.00D																										
Cylinder powers (DC)	-0.75, -1.25, -1.75	-0.75, -1.25, -1.75																										
Axes (degrees)	10-180, 10 degree steps	10-180, 10 degree steps																										

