2	
Number of subjects
 
The original protocol stated that up to 55 subjects should be enrolled, as the power calculation is based on 50 subjects completing the study.
 
As a result of a much higher number of ineligible subjects than expected, up to 65 subjects will now be enrolled. The intended number of subjects to complete remains 50.
 
As the lens SKU range is now increased, any subject who was originally ineligible owing to the required lens not being available, can now be re-enrolled and, if they wish to re-enrol, will be treated as a new subject (i.e. they will reconsent and re-attend the initial visit and so on).
 
Subjects found ineligible for other reasons will not be re-enrolled.
																											

Table 2: Changes to protocol C20-691 (version 1.0)

Document approved by:

Protocol amendment

Study title: The comparative clinical performance of two daily disposable toric contact lenses

The table below lists the changes to be implemented in this work:

New revision no.	Section/s to be Amended and details
1	
Inclusion criterion 1 originally read 'They are aged between 18 and 40 years old and have capacity to volunteer'.
 
Now amended to 'They are at least 18 years old and have capacity to volunteer'

2	
Number of subjects
 
The original protocol stated that up to 55 subjects should be enrolled, as the power calculation is based on 50 subjects completing the study. Protocol amendment 1 increased the maximum number to 65. In order to avoid falling short of the required number of completed subjects, owing to a high rate of subjects being found ineligible at the initial visit, the maximum number of subjects to be enrolled is increased to 70.

Table 1: Changes to protocol C20-691 (version 1.0)

Document approved by:

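### Does admitting cylinders to -2.50DC clash with an amended lens table that stops at -1.75DC?

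*Combined protocol and SAP*

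**What the plan says.** Section 2.1.3, criterion 6, sets the cylinder limit: "They have a cylindrical component of their contact lens prescription between -0.75DC and -2.50DC (inclusive". Criterion 7 adds that the subject must be satisfactorily fitted with the study lenses. Criterion 8 requires at least 6/12 in each eye at dispensing, using the powers that can be had.

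Table 2 in Section 2.6.1 is marked as still to be confirmed and is broken in the text available. It shows -0.75, -1.25 and -1.75 with one list of axes, and a further entry with its own shorter list: "2.25 10°, 20°, 90°, 160°, 170°, 180".

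Item 1 of the first protocol amendment announces "Both lenses are now available in all axes from 10 to 180 (10 degree steps" and substitutes a new table, whose cylinder row is "Cylinder powers (DC) -0.75, -1.25, -1.75 -0.75, -1.25, -1.75". Item 2 says "As the lens SKU range is now increased" and, on that ground, that "any subject who was originally ineligible owing to the required lens not being available, can now be re-enrolled".

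The second amendment edits one inclusion criterion, the age limit, which becomes "They are at least 18 years old and have capacity to volunteer", and raises the enrolment cap to 70. Neither amendment mentions -2.25 or touches criterion 6.

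At fitting, Section 3.2.2 works by "selecting the closest available lenses" for the prescription.

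**The concern.** Criterion 6 and the amended table are both in force, and read together they seem to disagree. The protocol admits a subject with a -2.50DC cylinder, but the strongest cylinder in the current table is -1.75DC. The sponsor replaced the table without revisiting the criterion, although it did revise another criterion in the second amendment. The amendment describes a wider range and reports no withdrawn power, so a reader cannot tell whether -2.25 was dropped, left out by mistake or lost in reading the PDF.

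If the power really is gone, some people who satisfy criterion 6 may consent, attend and then prove impossible to fit. Section 2.1.1 counts a subject as enrolled at consent, so each would use a place under the cap. The cap has already been raised twice, and both amendments give ineligibility as the reason.

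**Working it through.** **1. Distance between the criterion and each table.** Inputs: the limit in criterion 6 (2.50), the strongest power in Section 2.6.1 (2.25) and the strongest in the amended table (1.75).

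| Comparison | Arithmetic | Gap |
|---|---|---|
| Criterion 6 limit against Section 2.6.1 table | 2.50 - 2.25 | 0.25D |
| Criterion 6 limit against amended table | 2.50 - 1.75 | 0.75D |
| A -2.25DC prescription against amended table | 2.25 - 1.75 | 0.50D |

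The first row matters most. Even with -2.25 listed, the criterion went past the strongest lens. It was never a copy of the supply list; it is a bound on the prescription, to be met with the nearest lens. The documents set no tolerance in dioptres for that nearest lens, so a gap of 0.50D or 0.75D does not by itself make a subject ineligible. The tests the plan does set are fit and 6/12 acuity.

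**2. A -2.50DC subject followed through the plan, taking the amended table as printed.**

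- The subject meets criterion 6, consents and is enrolled (Section 2.1.1).
- At the initial visit both lens types are tried in the nearest available powers (Section 3.2.2).
- If the fit is unsatisfactory, criterion 7 fails. If acuity at dispensing is below 6/12 and no available power helps, criterion 8 fails. Section 2.2 then has the subject discontinued and replaced.
- If both are met, the subject is eligible and wears both lenses. The amended table lists the same three powers for each lens, and Section 3.2.2 asks for the same sphere and cylinder powers in both where possible. Any under-correction would then tend to be common to the two periods and would not favour one lens in a within-subject difference.

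**3. The sample size.** Section 1.6.1 gives 50 completers for 90% power, with a standard deviation of 1.5 for intra-subject differences and a difference of 0.7. It does not state alpha; two-sided 0.05 is assumed here.

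- Formula: n = (SD x (z(1 - alpha/2) + z(power)) / difference)^2
- n = (1.5 x (1.960 + 1.282) / 0.7)^2 = 48.2, rounded up to 49
- The paired t calculation gives 51, and power at 50 is 89.9%

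The plan's 50 is reproduced to within two subjects. No cylinder power enters the formula, so the answer is the same whichever table is right.

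**4. Room under the cap.** 70 - 50 = 20 enrolled subjects may fail screening or drop out before the target is at risk, against 55 - 50 = 5 at the start. The documents do not say how many ineligible subjects had cylinders beyond -1.75DC, so the share of the 20 that this mismatch might use cannot be estimated.

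**The case for a change.** The strongest case for acting is that the amended table is current text, not superseded text, so the disagreement with criterion 6 is live. The same three powers stand in two separate cells, so a reading error would have had to drop -2.25 twice. Criterion 8 leans on the available range, which is the very thing in doubt, so two sites could treat the same -2.25DC candidate differently. A person invited back under the re-enrolment rule for a lens that is not supplied would also take a second place.

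Part of this stands. The mismatch is there on the page, and if it is real it could cause avoidable screen failures.

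The rest is weaker. The table is demonstrably misread: the lens and material names are garbled. In Section 2.6.1 the -2.25 entry is separate from the other powers, and a separate line of that kind could have been missed in both columns. Different treatment by site is conjecture. Section 2.6.3 says that sites buy through their own accounts, not that the powers on offer differ between them, and all sites apply the same criteria 7 and 8. The re-enrolment wording covers anyone turned away because a lens was unavailable, which includes a subject refused for a -2.25 lens. Such a person reconsents and is assessed afresh, so at worst the visit is wasted.

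**Conclusion.** No change to the plan is needed. The criterion exceeds the amended table by up to 0.75D as printed, but it bounds prescriptions while the table lists lenses, and the two already differed by 0.25D in the unamended protocol. When the plan is followed as written, criteria 7 and 8, the nearest-lens rule and replacement under Section 2.2 keep the comparison sound. The primary outcome, its within-subject analysis and the 50 completers do not depend on which cylinder powers were supplied.

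The cost is at most an unknown number of screen failures within the 20 places between 50 completers and the cap of 70. No stated change would alter a result, because the documents do not show which of the two entries is off. What remains is clerical: look at the amended table in the source copy and, if -2.25 is missing there too, reconcile it with criterion 6.

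This rests on two assumptions: that sites apply criteria 7 and 8 as written, and that the two lenses come in the same cylinder powers, as the amended table shows.

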2.1.4 Exclusion criteria

Subjects will not be eligible to take part in the study if:

1. They have an ocular disorder which would normally contra-indicate contact lens wear.
2. They have a systemic disorder, which would normally contra-indicate contact lens wear.
3. They are using any topical medication such as eye drops or ointment.
4. They are aphakic.
5. They have had corneal refractive surgery.
6. They have any corneal distortion resulting from previous hard or rigid lens wear or have keratoconus.
7. They are pregnant or breastfeeding.
8. They have any ocular abnormality which would, in the opinion of the investigator, normally contraindicate contact lens wear.
9. They have eye or health conditions including immunosuppressive or infectious diseases, which would, in the opinion of the investigator, contraindicate contact lens wear or pose a risk to study personnel; or a history of anaphylaxis or severe allergic reaction.
10. They are currently wearing one of the study contact lenses.
11. They have taken part in any other contact lens or care solution clinical trial or research, within two weeks prior to starting this study.

2.2 Subject discontinuation

In general, subjects should be discontinued at any time, if it is in their best interests, as judged by the investigator. Reasons for this may include clinical signs of grade 3 or more, lack of motivation, discomfort, repeated refusal to follow instructions or the use of non-study products such as solutions or lenses. Subjects will be discontinued if a serious adverse event occurs or if they miss two or more planned consecutive visits. Subjects who fail to satisfy all the inclusion and exclusion criteria will be discontinued and replaced. Subjects may choose to leave the study at their own request. All discontinuations will be carefully recorded.

2.3 Safety parameters, adverse events and concurrent illnesses

The key safety parameters are the serious and significant ocular adverse events listed in [REDACTED] (adverse events are classified as 'serious', 'significant' or 'non-significant'). Clinical assessment is made at the study visit(s) for these parameters. The presence of an adverse event will be reported on the case report forms and those described as 'serious' or 'significant' will be detailed in the final report. Similarly, any concurrent illness that is likely to impact on the relevance and quality of the captured data will be noted on the case report form.

2.3.1 Investigator obligations

At all times the investigator will act in the best interest of the subject. Referral or treatment of an adverse event or other clinical finding should be initiated in the best clinical judgement of the investigator, irrespective of the participation in the clinical study.

2.3.2 Reporting obligations

In the case of a 'serious' or 'significant' adverse event, the investigator will notify Eurolens Research as soon as possible. The Principal Investigator will notify the Sponsor Contact Person as soon as possible following notification of the event. Manchester UREC and any regulatory authorities will be informed as required.

2.4 Study termination

If it becomes necessary to terminate the study earlier than planned, the Sponsor Contact Person will notify the Principal Investigator who will end the study with the cooperation of all sites. Manchester UREC will be informed. If the Principal Investigator becomes aware of any reason to terminate the study earlier than planned (e.g. reported unusual ocular findings or subject symptoms), the Principal Investigator will notify the Sponsor Contact Person to discuss the matter,

2.5 Protocol deviations

Any deviations from this protocol will be recorded and reported to the Sponsor Contact Person as appropriate. Manchester UREC will be informed as necessary.

2.5.1 Protocol amendments

Any amendments will be agreed between the Sponsor Contact Person and the Principal Investigator with the cooperation of all sites. Amendments will be recorded, identified and distributed. Approval from Manchester UREC will be obtained as necessary.

2.6 Study resources

Study products will be stored according to the manufacturer's product instructions.

2.6.1 Lenses

Details of the study lens are provided in Table 2. All lens types are CE marked. Initial lens selection will be as indicated by the manufacturer fitting guidelines.

	MyDay toric	DAILIES Total 1 toric
Manufacturer	CooperVision Inc	Acon
Material	Stenfcon A	Defcon A
EWC (%)	54%	Core Water Content (%) 33%; Surface Water Content (%) > 80%
BOZR (mm)	8.6	
Diameter (mm)	14.5	
Spherical powers (D)	Pano to -6.00	
Cylindrical powers (D)	-0.75; -1.25, -1.75; 10°, 20°, 70°, 80°, 90°, 100°, 110°, 160°, 170°, 180°	-2.25 10°, 20°, 90°, 160°, 170°, 180° 0°
Axes (degrees)		Lens parameters to be confirmed

Table 2: Study lenses.

2.6.1.1 Use of lenses

Both lens types will be worn on a daily wear, daily disposable basis (i.e. removed at end of day and discarded). Lenses should be worn for a minimum of eight hours per day, five days per week. The lenses are also to be worn for a minimum of two hours before attending the follow-up visits.

2.6.2 Care regimen

No care system will be used on this study.

2.6.3 Inventory control

Both lens types will be sourced by the respective sites based on their existing accounts and relationships with the two product manufacturers. All worn lenses will be discarded. Lenses of interest such as Product Quality Complaints (PCQ) which have been stored during the study, will be discarded on completion of the study report, unless advised otherwise by the Industrial Contact Person. Unworn lenses will be retained by the sites for use as they see fit. All used study products must be documented (Lot number; Expiry date etc.) in the study paperwork or case record form (CRF).

2.6.4 Clinical equipment

Clinical equipment is regularly maintained and calibrated as required. Standard operating procedures and international standards are used where appropriate.

2.7 Study control

This study is controlled by cross-comparison. Bias will be minimised by randomising the order of assessment.

2.8 Documentation

Documents related to this work that require archiving will be kept by Eurolens Research for a period of 20 years after completion of the final report. The Sponsor company's permission will be sought before the documents are destroyed.

2.9 Data collection and analysis

- a) At Eurolens Research, data collected in this work will be recorded on a custom-developed database and an established data trail. Data handling will include export of the study information from the clinical database into spreadsheet format for manipulation, followed by export into a statistical package for analysis. Most clinical data will be entered directly onto the electronic case report form and are considered to be source data.
- b) External sites will record study data on paper CRFs, which will be sent to Eurolens Research for data input and analysis. Paper CRFs are considered source data for the external sites. Personal identifiable information will not leave individual sites.

2.10 Study completion

The clinical phase of the study will be considered as complete when all subjects have attended their last visit.

2.11 Confidentiality

All matters related to this work will remain confidential within Eurolens Research, the external sites, the funding company and any regulatory authority (e.g. Manchester UREC). All sites will take reasonable steps to ensure that specific lens-related information is not passed on to study participants unless this is required for clinical management of an adverse event. Personal subject information will not be made available. To cater for this, subjects will only be referred by their unique identity number in the study report. The data activities of Eurolens Research are registered with the data protection officer at The University of Manchester.

2.12 Study monitoring

In order to provide quality control and quality assurance as part of this work, the study monitor will:

1. Liaise closely with the Principal Investigator.
2. Monitor and ensure the safety of the subjects.
3. Ensure that the investigation is being conducted according to the protocol.
4. Monitor and review (or oversee review of) the study records to ensure accuracy.
5. Document their observations and make them available to relevant authorised parties (e.g. Manchester UREC).

6. Implement the Eurolens Research clinical monitoring standard operating procedure.

2.13 Clinical trial registration

This study will be registered with clinicaltrials.gov in accordance with section 801 of the Food and Drug Administration (FDA) Act which mandates the registration of certain clinical trials of drugs and medical devices.

Section 3. Subject management

3.1 Visit scheduling

Subjects will be required to attend four visits – an initial visit, a dispensing visit and two follow-up visits, after one week of contact lens wear in each lens type. Acceptable date ranges are shown in Table 3.

Vst	Target	Allowable range
Initial	N/A	N/A
Dispensing 1	N/A	N/A
Follow-up 1/Dispensing 2	7 days from Dispensing 1	6-11 days from Dispensing 1
Follow-up 2	7 days from Dispensing 2	6-11 days from Dispensing 2

Table 3: Visits and allowable ranges.

